6.6 STATISTICAL SOFTWARE

The data will be extracted and imported into Stata (version 17.0 or higher). All analyses will be carried out in Stata (StataCorp LLC, College Station, TX, USA).

Canolfan Ymchwil Treialon

7.2 DATA MANAGEMENT PLAN

Data management plan: P:\152310305\PRONTO\eTMF\8.0 Data Management\8.1 Data Management \DOCUMENTS\DMP

7.3 TRIAL MASTER FILE AND STATISTICAL MASTER FILE

Trial master file: P:\152310305\PRONTO\eTMF

Statistical master file: P:\152310305\PRONTO\eTMF\8.0 Data Management\8.5 Statistics

7.4 OTHER SOPS OR GUIDANCE DOCUMENTS

Randomisation plan: P:\152310305\PRONTO\eTMF\8.0 Data Management\8.5 Statistics\ Randomisation

Interim SAP: P:\152310305\PRONTO\eTMF\8.0 Data Management\8.5 Statistics\Statistical Analysis Plan\Interim SAP

SAP DEVIATION LOG

Document number:	Document version:	
Reason for deviation:		

TPL/008/2(v1.0)

Canolfan Ymchwil Treialon

Deviations from the planned analyses:

- For the ED subgroup analysis, we have used the site's % of participants waiting greater than
 >12hours from decision to admit at the time of randomisation, rather than the tercile, to reflect the increasing ED crowding
- We have not calculated the MLE or UMVUE estimates described in section 6.2.1.2 as the IDMC decided to continue the trial after the interim analysis even though the trial could have stopped according to the stopping criteria described in section 3.5.2

The following post-hoc exploratory analyses have been conducted on the following dates to understand the mechanism behind the results:

24/06/24:

- Descriptive tabulation of antibiotics and broad-spectrum antibiotics by arm
- Descriptive tabulation of ventilation and vasopressor by arm
- Descriptive tabulation of the participant timeline/pathway by arm
- Descriptive tabulation of the co-primary outcomes (28-day mortality and IV abx within 3-hours) by arm and NEWS2 score
- Descriptive tabulation of the algorithm risk vs clinical risk assessment by arm and NEWS2

11/07/24:

- Breakdown of amoxicillin and co-amoxiclav by IV/oral in the descriptive table of antibiotics by arm
- Descriptive tabulation of non-antibiotics (e.g., antivirals, anti-parasitic etc.) prescribed by arm
- Descriptive tabulation of the 10 most frequent combinations of first 2 abx prescribed simultaneously
- Descriptive summary (median [IQR]) of the number of days on broad-spectrum abx per participant per arm
- Descriptive tabulation of the proportion of participants who received two narrow spectrum abx simultaneously as their first abx
- Descriptive tabulation of 28-day mortality by algorithm risk category by arm
- Descriptive summary of the mean days on any abx by algorithm risk category by arm
- Explore whether mortality (adjusted for NEWS2) differed by site using post estimation of random effects

15/08/24:

- Descriptive tabulation of the first prescription given by arm
- Post-hoc subgroup analysis (using same methods described in section 6.2.6) of time to IV (secondary outcome #1) by NEWS2
- Poisson regression analysis of days on IV/any abx in first 14 days
- Logistic regression analysis of whether IV abx was initiated within 12 hours

TPL/008/2(v1.0)

Canolfan Ymchwil Treialon

Short title: IS

: ISAP / SAP Template

- Logistic regression analysis of whether IV abx was initiated within 7-days
- Descriptive summaries of the following, to explore whether the treatment pathway may have changed between the arms
 - \circ ~ Time from triage (+/- randomization) to prescription of antibiotics
 - \circ ~ Time from triage (+/- randomization) to administration of antibiotics
 - \circ \quad Time between prescription and administration of antibiotics
 - \circ ~~ % blood cultures taken in first 24 hours (No other measure in CRF)
 - Broad spectrum Abx (Watch/Reserve) vs narrow spectrum (Access)
 - Initial Diagnosis Infection vs Not Infection
 - Cause of Death
 - Time to HDU/ITU admission
 - Broad spectrum Abx (Watch/Reserve) vs narrow spectrum (Access)
 - Abx choice Compare distribution of No Antibiotics> PO>IV Narrow>IV broad
 - % Microbiology tests in first 24 hours (Blood cultures only)
 - % Microbiology tests in first 24 hours (Any)
 - \circ ~~ % Any antimicrobial resistance detected, if yes which by %
 - Duration of antibiotics (initial course started within 24 hours of attendance)
 - Length of hospital stay
 - o % No antibiotics vs any antibiotics
 - % Late course of antibiotics (2-28 days)
 - Time to late antibiotics
 - % Readmitted to hospital
- Descriptive summary of the days on no abx, oral, iv broad, iv narrow, combination for each NEWS score and arm

05/09/24

- Tabulate first prescription within 24 hours from triage by arm
- Tabulate arm by final diagnosis with mortality in the cells infection vs non infection
- Tabulate deaths in withdrawals by arm

19/09/24

- Tabulate 28-day mortality in different algorithm adherence groups including the discordant groups (low clinical risk & high algorithm risk and vice versa) (unexpected vs expected PCT result)
- A logistic regression analysis of trial arm's effect on being alive and not readmitted at 90 days
- Subgroup analysis (as described in section 6.2.6) of grading of clinician conducting assessment
- Subgroup analysis (as described in section 6.2.6) of index of deprivation decile
- Tabulate time between 1st and 2nd assessment overall, by arm and by NEWS2
- Time series plot of ED crowding by site
- Subgroup analysis (as described in section 6.2.6) of initial diagnosis of LRTI/CAP vs all other initial diagnoses

Canolfan Ymchwil Treialon

Short title:	ISAP / SAP Template
--------------	---------------------

- Subgroup analysis (as described in section 6.2.6) of initial diagnosis of respiratory infection vs all other initial diagnoses

02/12/24

- Descriptive comparison of initial diagnosis and final diagnosis by arm using Sankey diagrams

09/12/24

- Descriptive tabulation of 28-day morality by arm by type of abx received within 12 hours

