It has been recognised that the option to stop the trial early in sequential designs introduces bias to the standard maximum likelihood estimator (MLE) (Cox, 1952). Therefore, we will also calculate unconditional bias-adjusted point estimates. We will derive the bias-adjusted maximum likelihood estimates proposed by Whitehead, by subtracting an estimate of the bias from the MLE (Whitehead, 1986). We will also calculate the uniformly minimum variance unbiased estimator (UMVUE) using the Rao-Blackwell technique. We will calculate the unconditional bias-adjusted point estimates, as we want to determine the point estimates regardless of the stage at which the trial stops. We are interested in the bias as averaged over all possible stopping times, weighted by the respective stage-wise stopping probabilities (Robertson et al., 2023, Grayling & Wason, 2022).

Table 6: Summary of analyses of primary outcomes

Outcome	Analysis	Covariates
	Primary analysis:	Trial arm and baseline NEWS2

Canolfan Ymchwil Treialon

IV antimicrobial	Two-level logistic regression	Trial arm, baseline NEWS2, age,
initiation at 3 hours		number of comorbidities and gender
(superiority)	Secondary analysis:	Trial arm and baseline NEWS2
	Two-level logistic regression with	Trial arm, baseline NEWS2, age,
	bias-adjusted point estimates	number of comorbidities and gender
	Subgroup analyses:	Trial arm, baseline NEWS2, and the
	Two-level logistic regression	organ system of the infection (lower
	(interaction test by model	urinary tract, lower respiratory, intra-
	comparison)	abdominal, bacteraemia, skin, soft
		tissues, etc.)
		Trial arm, baseline NEWS2, and risk
		category based on NEWS2 score at
		baseline (≤4, 5-6 and ≥7)
		Trial arm, baseline NEWS2, and
		managed as suspected COVID-19
		during admission (yes/no)
		Trial arm, baseline NEWS2, and has a
		positive COVID-19 test result +/- 5 days
		from admission (yes/no)
		Trial arm, baseline NEWS2, and PCT
		machine used at the time of
		recruitment (BRAHMS PCT-
		direct/PathFast BRAHMS PCT)
		Trial arm, baseline NEWS2, and
		recruitment date (before 01/12/21,
		between 01/12/21 and 30/11/22, after
		30/11/22)
		Trial arm, baseline NEWS2, and level of
		site ED crowding (upper, middle and
		lower tercile of national monthly
		figures)
	Complier average causal effect	Trial arm, baseline NEWS2, and
	(CACE)	intervention adherence
28-day mortality	Primary analysis:	Trial arm and baseline NEWS2

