6.2.6 SUBGROUP ANALYSES

We will conduct seven separate subgroup analyses, stratified by:

- The organ system of the infection (initial working diagnosis):
 - Upper respiratory tract infection
 - Skin/soft tissue infection
 - Urinary tract infection/urosepsis
 - Central nervous system infection
 - Gastrointestinal tract/abdominal infection
 - Bone/joint/muscle infection
 - Lower respiratory tract infection/community-acquired pneumonia
 - Sepsis (unknown source)
 - Other infections
 - Not infection
- Risk category based on NEWS2 score at baseline:
 - ≤4
 - 5-6
 - ≥7
- Managed as suspected COVID-19 during admission:
 - Yes
 - No
- Positive COVID-19 test result +/- 5 days from admission:
 - Yes
 - No
- PCT machine used at time of recruitment:
 - BRAHMS PCT-direct

TPL/008/2(v1.0)

Canolfan Ymchwil Treialon

Short title: ISAP / SAP Template

- PathFast BRAHMS PCT
- Recruitment date:
 - Before 1st December 2021
 - Between 1st December 2021 and 30th November 2022
 - After 30th November 2022
- Level of site ED crowding (percentage of patients who spent >12 hours from decision to admit to admission) at time of randomisation:
 - Upper tercile of national monthly figures
 - Middle tercile of national monthly figures
 - Bottom tercile of national monthly figures

We will investigate whether the treatment effect varies between subgroups by including the subgroup variable as a covariate in the main analysis model, both with and without a treatment-arm interaction term. The models with and without the interaction term will be compared using a likelihood-ratio test (LRT). We will report the LRT χ^2 statistic and illustrate the direction of the subgroup effect using forest or interaction plots.

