We will also assess whether adherence to the intervention varies according to levels of ED crowding at the time of randomisation. We will conduct a two-level logistic regression (patients nested within sites) with algorithm adherence (yes/no) as the outcome variable and the level of ED crowding as the explanatory variable, controlling for baseline NEWS2 score (minimisation variable). NHS England publishes monthly A&E attendances and emergency admissions data. We will calculate the percentage of emergency admission patients who spent >12 hours from decision to admit to admission per month per site and compare these to the national monthly figures. We will rerun the co-primary analyses for subgroups of the least, middle, and most crowded EDs. As an exploratory analysis we may include ED crowding as an additional covariate and include time varying interaction terms. If the data allows, we may also explore the effect of daily ED crowding levels on the co-primary outcomes for a subgroup of sites.

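### Crowding subgroup: the deviation log replaces national monthly terciles with a site percentage that rises over the trial, so the arm-by-crowding interaction is partly confounded with calendar time

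*SAP*

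**What the plan says.** Section 6.2.6 defines the crowding variable as "Level of site ED crowding (percentage of patients who spent >12 hours from decision to admit to admission) at time of randomisation", in three bands, the top one being "Upper tercile of national monthly figures". Its closing paragraph says the site figure is calculated "per month per site and compare these to the national monthly figures".

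The interaction is tested by "including the subgroup variable as a covariate in the main analysis model, both with and without a treatment-arm interaction term", with the two models compared by a likelihood-ratio test. Table 6 in section 6.2.1.2 gives the covariates for this subgroup as "Trial arm, baseline NEWS2, and level of" site crowding, so recruitment date is not in the model. Recruitment date is a separate subgroup with three bands, the middle one being "Between 1st December 2021 and 30th November 2022". Time appears in the crowding text only as an exploratory option: "we may include ED crowding as an additional covariate and include time varying interaction terms".

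The deviation log after section 7.4 states that the site's percentage was used "at the time of randomisation, rather than the tercile, to reflect the increasing ED crowding". It does not say whether the percentage was entered linearly or cut into bands, whether any time term was added, or whether the tercile version will still be reported.

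**The concern.** A band set against the national figure for the same month asks whether a department was more or less crowded than others at that time. A trend common to all departments cancels out. The raw percentage keeps that trend, and the log gives the trend as the reason for the change. Late recruits then tend to have high values and early recruits low ones, so the variable partly measures date of recruitment.

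The PCT effect could plausibly have changed over the trial. The SAP itself plans subgroups by recruitment date, PCT machine and COVID-19 status; the first is calendar time and the other two may well vary with it. At stake is the attribution of an interaction: a report could say that PCT guidance works differently in crowded departments when what changed was the period.

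**Working it through.** The SAP gives no figure for the crowding analysis, so there is none to reproduce. The check has two parts.

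**Which tercile was meant.** Section 6.2.6 pairs monthly site figures with monthly national figures, but does not say outright that the cut points are reset each month. The log's reason helps. Terciles pooled over all months would already show rising crowding, so there would be no need to drop them on that ground. Same-month terciles are the natural reading, though an inferred one.

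**How much drift could pass as crowding.**

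Assumed, because the SAP does not give them: N = 7,000 (near the 7,002 of section 3.3), 20 sites, 36 months, between-site SD 8 points, within-site SD 4 points, linear rise R over the trial, and a true log-odds effect that drifts by δ with time and does not depend on crowding.

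1. Share of variance in the raw percentage due to time: ρ² = (R²/12) / (R²/12 + 8² + 4²).
   - R = 10: 8.33/88.33 = 9.4%, ρ = 0.307.
   - R = 20: 33.33/113.33 = 29.4%, ρ = 0.542.
2. Spurious interaction per SD of crowding: b = δρ/√12. For same-month terciles the correlation with time is zero, so b = 0.
3. Standard error with 1:1 arms: 2/√(N p(1−p)). At p = 50% it is 2/√1750 = 0.0478. At p = 15% (the control mortality assumed in section 3.3) it is 2/√892.5 = 0.0669.
4. Two-sided 5% rejection: P(|Z + b/SE| > 1.96).

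| Rise R | Drift δ | b | Rejection, 50% outcome | Rejection, 15% outcome |
|---|---|---|---|---|
| 10 | 0.4 | 0.0355 | 12% (b/SE 0.74) | 8% (0.53) |
| 10 | 0.8 | 0.0709 | 32% (1.48) | 19% (1.06) |
| 20 | 0.4 | 0.0626 | 26% (1.31) | 15% (0.94) |
| 20 | 0.8 | 0.1252 | 75% (2.62) | 47% (1.87) |

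Simulation with the same numbers of patients, sites and months agrees. For a 50% outcome the raw-percentage test rejected in 13–29% of trials at δ = 0.4 and 28–75% at δ = 0.8. For 15% mortality the figures were 3–15% and 20–49%. The 3% is below the nominal level, so at the weakest setting no inflation is visible. Same-month terciles, or the raw percentage with time and arm-by-time added, stayed near 5%. Without drift nothing was inflated.

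The 50% rate is an assumption. With the 90% that section 3.3 assumes for antibiotic treatment, SE = 2/√630 = 0.0797, and the four cases become 7%, 15%, 12% and 35%.

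**What the drifts mean.** At a 50% control rate, δ = 0.4 running from −0.4 to 0 takes the risk difference from about −10 points to 0; δ = 0.8 running from −0.6 to +0.2 takes it from about −15 to +5. Centred on 15% mortality, δ = 0.4 moves intervention-arm mortality from 12.6% to 17.7%, and δ = 0.8 from 10.6% to 20.8%.

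**What the raw percentage still detects.** In a further simulation (300 runs per setting, event rate about 15%), crowding relative to the same month was made the true modifier, at 0.3 log-odds per SD. The raw-percentage test still rejected in 98%, 95% and 66% of runs. The settings had rises of 8, 20 and 30 points and between-site SDs of 8, 8 and 4, with month explaining 7%, 33% and 72% of the variance.

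**The case against.** Absolute crowding is a defensible exposure. A same-month rank can give one label to departments with very different waits early and late, and it discards real change over time. If rising crowding itself alters the PCT effect, adjusting for arm-by-time removes part of the signal. This stands. It supports showing the raw percentage, but not leaving the planned analysis out.

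The drifts are also large: at δ = 0.4 the whole 10-point design effect on antibiotic initiation disappears during the trial, and no evidence of drift is cited. Drift is, moreover, tested separately. With three equal recruitment-date bands and N = 7676 × 0.95 = 7,292, the non-centrality is (N × 0.25/4) × (2δ²/27). That is 5.4 at δ = 0.4 and 21.6 at δ = 0.8, or about 54% and 99% power on 2 degrees of freedom. A drift big enough to mislead would often show there first. This stands too, and is why the two results should be read together. It does not make the crowding test itself separable from time.

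The model actually fitted is unknown, since the log gives one line. The absence of a time term is taken from the planned covariate list.

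A reader might infer that the crowding test has become a test of calendar time. The documents do not support that: the percentage is site-specific, and differences between sites and fluctuation within sites remain.

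**Conclusion.** The point holds as partial confounding of one subgroup interaction. The log replaces a measure most naturally read as relative to the same month with one that rises over the trial, and the listed model does not separate crowding from time. Under the assumed values the false attribution rate is roughly 3–30% at a log-odds drift of 0.4 and 20–75% at 0.8 for rises of 10 to 20 points, lower if the IV initiation rate is near 90%, and about 5% with no drift. These figures illustrate the risk; the SAP gives neither the trend, the site spread nor the drift.

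Two further inferences would go too far. The co-primary conclusions are not biased, because the arm comparison is protected by randomisation and only the explanation of an interaction is at risk. Nor is the planned definition certainly free of the problem: if the terciles were pooled over months, it would carry the trend as well.

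**What to change.** - Report the pre-specified tercile analysis for both co-primaries beside the raw-percentage one, state that the cut points are same-month (or correct this if they are not), and label the raw-percentage analysis as a deviation.
- Add a raw-percentage version with recruitment date and arm-by-recruitment-date in both models compared, so that the likelihood-ratio test concerns crowding within period.
- State in the log whether the percentage was linear or banded, which covariates were fitted, and which bands serve the three crowding strata in which section 6.2.6 reruns the co-primary analyses.
- Read the crowding result together with the recruitment-date subgroup before attributing any interaction to crowding.

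The cost is small: the terciles rest on published monthly figures and recruitment date is already an analysis variable. The time-adjusted test may lose a little power, and it removes part of any effect that runs through rising crowding itself, so adjusted and unadjusted versions should both be shown.

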8. APPENDICES

- 8.1 Dummy tables
- 8.1.1 Primary outcomes

Table A1 – Adherence to PCT-guided algorithm

		Cli	nical risk assessme	ent	
	Risk	Low	Low/medium	Medium	High
	Low	N =			
Algorithm	Low/medium				
	Medium				
	High				

Table A2 – Analysis populations defined by adherence to intervention.

	Level	n/N (%)
PCT test result available	Yes	
	No	
	Missing	
PCT test result considered in clinical decision making	Yes	

TPL/008/2(v1.0)

Canolfan Ymchwil Treialon

Short title:	ISAP / SAP Template

	No	
	Missing	
Algorithm adhered to	Yes	
	No	
	Missing	

Table A2 – Primary outcome analysis results

Outcome	Analysis	Treatment effect estimate [95% CI]	p-value
IV antimicrobial initiation	Primary	RD =	
at 3 hours (superiority) ^(a)	Adjusted for covariates	RD =	
	Bias-adjusted	RD =	
	CACE	RD =	
28-day mortality (non-	Primary	RD =	
inferiority) ^(a)	Adjusted for covariates	RD =	
	Bias-adjusted	RD =	
	CACE	RD =	
CI = confidence interval, RD = ris Analysis method: (a) multilevel Confidence intervals are two-sic	logistic regression.	d for 28-day mortality.	

Covariates in all models: baseline NEWS2.

8.1.2 Secondary outcomes

Table A3 – Secondary outcome analysis results

	Outcome	Analysis	Treatment effect estimate [95% CI]	p-value
1	Time until initiation of IV antibiotic therapy ^(a)	Primary	HR =	
		Adjusted for covariates	HR =	
2	Late IV antibiotic initiation – antibiotics commenced after 3	Primary	OR =	
	hours ^(b)	Adjusted for covariates	OR =	

TPL/008/2(v1.0)

Canolfan Ymchwil Treialon

Short title: ISAP / SAP Template

		1	I I
3	Number of days on IV antibiotics (during admission) ^(a)	Primary	IRR =
		Adjusted for covariates	IRR =
	Number of days on IV antibiotics $(1 + 1)^{(2)}$	Primary	IRR =
	(total over first 28 days) ^(a)	Adjusted for covariates	IRR =
4	Number of days on any antibiotic	Primary	IRR =
	(during admission) ^(a)	Adjusted for covariates	IRR =
	Number of days on any antibiotic	Primary	IRR =
	(total over first 28 days) ^(a)	Adjusted for covariates	IRR =
5	Number of days on broad-	Primary	IRR =
	spectrum antibiotics (IV and oral) (during admission) ^(a)	Adjusted for covariates	IRR =
	Number of days on broad-	Primary	IRR =
	spectrum antibiotics (IV and oral) (total over the first 28 days) ^(a)	Adjusted for covariates	IRR =
6	ICU or HDU admission – at any	Primary	OR =
	point during admission ^(b)	Adjusted for covariates	OR =
7	Length of ICU/HDU stay ^(a)	Primary	IRR =
		Adjusted for covariates	IRR =
8	Length of hospital stay ^(a)	Primary	IRR =
		Adjusted for covariates	IRR =
9	Adverse antibiotic outcomes ^(b)	Primary	OR =
		Adjusted for covariates	OR =
10	Readmission to the hospital	Primary	OR =
	within 90 days ^(b)	Adjusted for covariates	OR =
11	Mortality within 90 days ^(b)	Primary	OR =
		Adjusted for covariates	OR =
	Mortality within 90 days - time	Primary	HR =
	until death ^(a)	Adjusted for covariates	HR =
12	Health utility (EQ-5D-5L) at 28	Primary	MD =
	days ^(c)	Adjusted for covariates	MD =
		Primary	MD =

Canolfan Ymchwil Treialon

Short title: ISAP / SAP Template

	Health utility (EQ-5D-5L) at 28 days ^(c)	Adjusted for covariates	MD =
	Health utility (EQ-5D-5L) at 90	Primary	MD =
	days ^(c)	Adjusted for covariates	MD =
	Health utility (EQ-5D-5L) at 90	Primary	MD =
	days ^(c)	Adjusted for covariates	MD =
Analys	onfidence interval, HR = hazard ratio, Ol sis method: (a) cox regression, (b) logist iates in all models: baseline NEWS2.		

8.1.3 Subgroup analyses

Table A4 – Subgroup analyses of primary outcomes

Outcome	Subgroups	LRT χ² (df)	p-value
IV antimicrobial	The organ system of the infection		
initiation at 3 hours (superiority) ^(a)	Risk category based on NEWS2 score at baseline		
	Managed as suspected COVID-19 during admission		
	Positive COVID-19 test result +/- 5 days from admission		
	PCT machine used		
	Recruitment date		
	Level of ED crowding		
28-day mortality	The organ system of the infection		
(non-inferiority) ^(a)	Risk category based on NEWS2 score at baseline		
	Managed as suspected COVID-19 during admission		
	Positive COVID-19 test result +/- 5 days from admission		
	PCT machine used		
	Recruitment date		
	Level of ED crowding		
Analysis method: (a) mu Covariates in all models	I Itilevel logistic regression. Interaction tests by model comp : baseline NEWS2.	arison.	-

TPL/008/2(v1.0)

Canolfan Ymchwil Treialon

Short title: ISAP / SAP Template
